- Wilson's disease and hemochromatosis
- Nonalcoholic fatty liver disease including steatohepatitis
- Non-hepatic causes (eg, rhabdomyolysis, hemolysis)

If investigational product(s) is/are withheld, the subject is to be followed for possible drug induced liver injury (DILI) according to recommendations in the last section of this appendix.

Rechallenge may be considered if an alternative cause for impaired liver tests (ALT, AST, ALP) and/or elevated TBL, is discovered and the laboratory abnormalities resolve to normal or baseline (see next section in this appendix).

Table 11-2. Conditions for Withholding and/or Permanent Discontinuation of Amgen Investigational Product and Other Protocol-required Therapies Due to Potential Hepatotoxicity

Analyte	Temporary Withholding	Permanent Discontinuation
TBL	> 3x ULN at any time	> 2x ULN
INR	--	> 1.5x (for subjects not on anticoagulation therapy)
AST/ALT	> 8x ULN at any time > 5x ULN but < 8x ULN for ≥ 2 weeks > 5x ULN but < 8x ULN and unable to adhere to enhanced monitoring schedule > 3x ULN with clinical signs or symptoms that are consistent with hepatitis (such as right upper quadrant pain/tenderness, fever, nausea, vomiting, and jaundice)	OR AND In the presence of no important alternative causes for elevated AST/ALT and/or TBL values > 3x ULN (when baseline was < ULN)
ALP	> 8x ULN at any time	--

ALP = alkaline phosphatase; ALT = alanine aminotransferase; AST = aspartate aminotransferase; INR = international normalized ratio; TBL = total bilirubin; ULN = upper limit of normal

Criteria for Rechallenge of Amgen Investigational Product and Other Protocol-required Therapies After Potential Hepatotoxicity

The decision to rechallenge the subject is to be discussed and agreed upon unanimously by the subject, investigator, and Amgen.

If signs or symptoms recur with rechallenge, then olpasiran is to be permanently discontinued. Subjects who clearly meet the criteria for permanent discontinuation (as described in [Table 11-2](#)) are never to be rechallenged.

Drug-induced Liver Injury Reporting and Additional Assessments

Reporting

To facilitate appropriate monitoring for signals of DILI, cases of concurrent AST or ALT and TBL and/or INR elevation, according to the criteria specified in the above, require the following:

- The event is to be reported to Amgen as a serious adverse event within 24 hours of discovery or notification of the event (ie, before additional etiologic investigations have been concluded)

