- The appropriate Case Report Form (CRF) (eg, Events CRF) that captures information necessary to facilitate the evaluation of treatment-emergent liver abnormalities is to be completed and sent to Amgen

Other events of hepatotoxicity and potential DILI are to be reported as serious adverse events if they meet the criteria for a serious adverse event defined in Section 11.4.

Additional Clinical Assessments and Observation

All subjects in whom investigational product(s) or protocol-required therapies is/are withheld (either permanently or conditionally) due to potential DILI as specified in Table 11-2 or who experience AST or ALT elevations > 3 x upper limit of normal (ULN) or 2-fold increases above baseline values for subjects with elevated values before drug are to undergo a period of “close observation” until abnormalities return to normal or to the subject’s baseline levels. Local laboratory results are required in the event that additional tests are needed for DILI criteria.

Assessments that are to be performed during this period include:

- Repeat AST, ALT, ALP, bilirubin (BIL) (total and direct), and INR within 24 hours
- In cases of TBL > 2 x ULN or INR > 1.5 , retesting of liver tests, BIL (total and direct), and INR is to be performed every 24 hours until laboratory abnormalities improve

Testing frequency of the above laboratory tests may decrease if the abnormalities stabilize or the investigational product(s) or protocol-required therapies has/have been discontinued AND the subject is asymptomatic.

Initiate investigation of alternative causes for elevated AST or ALT and/or elevated TBL.

The following are to be considered depending on the clinical situation:

- Complete blood count with differential to assess for eosinophilia
- Serum total immunoglobulin (Ig)G, anti-nuclear antibody anti-smooth muscle antibody, and liver kidney microsomal antibody-1 to assess for autoimmune hepatitis
- Serum acetaminophen (paracetamol) levels
- A more detailed history of:
 - Prior and/or concurrent diseases or illness

- Exposure to environmental and/or industrial chemical agents
- Symptoms (if applicable) including right upper quadrant pain, hypersensitivity-type reactions, fatigue, nausea, vomiting and fever
- Prior and/or concurrent use of alcohol, recreational drugs and special diets
- Concomitant use of medications (including non-prescription medicines and herbal and dietary supplements), plants, and mushrooms
- Viral serologies

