9.6.2 Laboratory Test Results

Selected laboratory parameters will be summarized using descriptive statistics at scheduled visits. Laboratory shift tables using the CTCAE v5.0 or later grading will be used for analytes of interest, when applicable. The results will be based on the maximum (e.g., worst) shift from baseline to the EOS.

In addition, creatine kinase (CK) and liver function test (LFT) abnormalities will be assessed by the incidence overall and by visits of the following categories:

- CK > 5 x ULN
- CK > 10 x ULN
- ALT or AST > 3 x ULN
- ALT or AST > 5 x ULN

- Total bilirubin > 2 x ULN
- (ALT or AST > 3 x ULN) and Total bilirubin > 2 x ULN and Alkaline Phosphatase <2 x ULN

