Appendix A. Analytical Study Week Assignments

Selected endpoints will be summarized by scheduled study visits in descriptive analyses. Since the actual visits may not exactly coincide with their scheduled visit day, the actual visit day is mapped to the study visit generally by non-overlapping consecutive intervals covering the entire time continuum. The mapping intervals for all distinct schedules are summarized in the following table.

Handling multiple records assigned to an analytical study week:

If there is more than one record in a study week interval, the analytical record for that specific study week will be defined as the record closest to the scheduled visit day of that specific study week ($7 \times \text{study week} + 1$). If two records are equidistant from the scheduled day, then the earlier record will be chosen. If there are multiple records on the same day, the last record will be used.

Analytical Study Week	Scheduled Visit Day	Physical, Neurological, and Muscular Examination, Vital Signs, Urine Pregnancy Test, Anti-Olpasiran-Antibody, PROMIS General Health	Physical measurement (weight only)	Fasting Lipids and Lp(a)	Glucose, ApoA1, ApoB, VLDL-C, Coagulation, Hematology, Hemoglobin A1C, Chemistry including hs-CRP, eGFR, Urinalysis
Day 2	2			(1, 15]	
Week 4	29			(15, 42]	(1, 56]
Week 8	57			(42, 70]	
Week 12	85	(1, 126]		(70, 98]	(56, 126]
Week 16	113			(98, 126]	
Week 20	141			(126, 154]	
Week 24	169	(126, 210]		(154, 182]	(126, 210]
Week 28	197			(182, 210]	
Week 32	225			(210, 238]	
Week 36	253	(210, 294]		(238, 266]	(210, 294]
Week 40	281			(266, 294]	
Week 44	309			(294, 322]	
Week 48	337	(294, 420]	(1, 420]	(322, 378]	(294, 420]
Week 60	421			(378, 462]	
Week 72	505	(420, 546]	(420, 546]	(462, 546]	(420, 546]
Week 84	589			(546, 630]	
Q12W ^a	n*7+1			((n-6)*7, (n+6)*7]	
> Week 72	Scheduled visit day	> 546	> 546	.. ^b	> 546

^a For Q12W scheduled visit, week n can have possible values of 96+12*m, where m=0, 1, 2, 3, ... until the subject **has completed study** or subject has discontinued from the study.

^b For Lipids and Lp(a), all visits occurred after week 84 will be mapped to Q12W window.

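### The SAP's combined liver row omits the INR limb and adds an ALP ceiling relative to the protocol's liver-injury criterion, and the record rules behind the liver counts are incomplete

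*SAP*

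**What the plan says.** SAP 9.6.2 states that CK and liver test "abnormalities will be assessed by the incidence overall and by visits of the following categories". The liver categories are ALT or AST above 3x and above 5x ULN, total bilirubin above 2x ULN, and one combined category: "ALT or AST > 3 x ULN) and Total bilirubin > 2 x ULN and Alkaline Phosphatase <2 x ULN". For the laboratory shift tables, the same section adds: "The results will be based on the maximum (e.g., worst) shift from baseline to the EOS". It makes no such statement for the threshold categories.

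Protocol 11.7 (Appendix 7), Table 11-2, bases permanent discontinuation on total bilirubin above 2x ULN or INR "> 1.5x (for subjects not on anticoagulation therapy"), together with AST/ALT above 3x ULN when baseline was below ULN, and no important alternative cause. The permanent-discontinuation column has no ALP entry. The reporting text below the table requires expedited reporting as a serious adverse event for "cases of concurrent AST or ALT and TBL and/or INR elevation, according to the criteria specified in the above".

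The same appendix calls for repeat liver tests and INR within 24 hours. When bilirubin exceeds 2x ULN or INR exceeds 1.5, retesting "is to be performed every 24 hours until laboratory abnormalities improve". Local laboratories may supply these follow-up results (Protocol 11.2 and 11.7).

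SAP Appendix A governs summaries by scheduled visit. When several records fall in one window, "the analytical record for that specific study week will be defined as the record closest to the scheduled visit day".

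**The concern.** Protocol 2.3 names liver enzyme elevation as one of only two potential risks of olpasiran. The combined row is the only planned laboratory summary that joins transaminases with bilirubin. Single-analyte rows and single-analyte shift tables cannot show that two abnormalities occurred together. If that row uses a narrower laboratory pattern than the protocol's reporting rule, its count cannot be reconciled with the cases reported under that rule.

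There is also a question of which records are counted. Close observation produces off-schedule samples, sometimes daily and sometimes from a local laboratory. The by-visit rule selects on closeness to the scheduled day, not on severity, and the overall count has no stated rule. Two programmers could follow the SAP and produce different liver tables.

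**Working it through.** The plan gives no liver event rate or liver-specific figure to reproduce, so the check compares definitions and then applies the window rule to an example.

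**1. Definitions.** Inputs are Protocol Table 11-2 with its reporting text, and SAP 9.6.2. The extracted table is broken, but the reporting text independently confirms that bilirubin and INR are alternatives. Fix AST/ALT above 3x ULN and assume that the protocol's baseline, anticoagulation and alternative-cause conditions are met. Three yes/no items remain, giving 2 × 2 × 2 = 8 patterns.

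| TBL > 2x | INR > 1.5 | ALP ≥ 2x | Protocol pattern | SAP combined row |
|---|---|---|---|---|
| no | no | no | no | no |
| no | no | yes | no | no |
| no | yes | no | yes | **no** |
| no | yes | yes | yes | **no** |
| yes | no | no | yes | yes |
| yes | no | yes | yes | **no** |
| yes | yes | no | yes | yes |
| yes | yes | yes | yes | **no** |

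Six patterns meet the protocol's limbs. The SAP row catches 2 and misses 6 − 2 = 4: two through INR alone, and two with raised bilirubin and ALP at or above 2x ULN. All six satisfy the separate row "ALT or AST > 3 x ULN", and the last two missed patterns also satisfy the bilirubin row.

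**2. The other direction.** The SAP row has no baseline or alternative-cause condition. Exclusion criterion 202 sets its screening limit at AST/ALT above 3x ULN, so a subject may enter with a value between 1x and 3x ULN. Such a subject, or one with viral hepatitis found later, can be counted in the SAP row without meeting the protocol's permanent-discontinuation criterion.

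**3. Windows.** Appendix A's column for chemistry and coagulation gives these widths in days: week 4, 56 − 1 = 55; week 12, 126 − 56 = 70; weeks 24 and 36, 210 − 126 = 294 − 210 = 84; weeks 48 and 72, 420 − 294 = 546 − 420 = 126. Each window yields one record.

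Illustrative subject (assumed values, in multiples of ULN), with week 24 scheduled on day 7 × 24 + 1 = 169:

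- Day 169: ALT 3.4, TBL 1.4
- Day 172: ALT 6.0, TBL 2.6, ALP 1.4

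Distances from day 169 are 0 and 3 days, so the rule keeps day 169.

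| Row | By visit, week 24 | Overall, if any record counts |
|---|---|---|
| ALT or AST > 3x | yes | yes |
| ALT or AST > 5x | no | yes |
| TBL > 2x | no | yes |
| Combined | no | yes |

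For a single-analyte row, the closest record can never exceed the worst record in the same window, so the by-visit count can only equal or fall below a worst-value count.

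**4. Scale.** With about 58 subjects per arm, one case is 1/58 = 1.7 percentage points.

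**The case against.** The strongest reply is that nobody is lost. A reader might infer that a subject permanently stopped for hepatotoxicity could be absent from the liver tabulation altogether. The documents do not support that. The stopping pattern requires AST/ALT above 3x ULN, which is a row of its own with no ALP or INR condition. Appendix A is written for summaries by scheduled visit, and nothing extends it to the overall incidence. These cases must also be reported as serious adverse events. SAP 9.6.1 tabulates serious events, events leading to discontinuation, and liver and coagulation events of interest, and SAP 9.2 tabulates discontinuation by reason. An unblinded Data Review Team also reviews serious events and relevant laboratory results (Protocol Appendix 3). All of this stands.

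It is also fair to say that the threshold rows already go beyond Protocol 9.4.2.3.2, which asks only for summaries by visit and shifts to the worst grade. The ALP ceiling may serve a purpose that the SAP does not state, which is a reason to keep the existing row.

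The reply does not cure the gap. Adverse event tables rest on coded terms and cannot show how many subjects met the protocol's laboratory pattern. The SAP does specify the laboratory source elsewhere (central values for lipids, SAP 5.2 and 5.3), so its silence on local and unscheduled liver values is a real omission.

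**Conclusion.** The point holds as a mismatch in one table row and an incomplete record rule. The combined row catches two of the six patterns that meet the protocol's laboratory limbs. The by-visit counts can lose an off-schedule peak. The records behind the overall count, and the meaning of concurrent, are not stated. The result rests on the reading of Table 11-2 given above and on Appendix A applying to the by-visit liver counts. How many subjects would be affected cannot be estimated from the documents.

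Three further inferences should be resisted:

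- That the error always runs toward under-reporting. The SAP row lacks the protocol's baseline and alternative-cause conditions, so the definitions differ in both directions.
- That the peak is usually the discarded record. This depends on sampling days: with a visit window of ±3 days, a scheduled sample on day 166 and a repeat on day 169 would leave the repeat as the record kept.
- That phase 3 dose choice turns on this table. The protocol ties dose selection to the interim analysis, a committee reviewing efficacy data, and an exposure-response analysis (Sections 4.1 and 6.4.2.2, Appendix 3). It mentions safety results only in general terms.

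This is a worthwhile, inexpensive improvement and not a flaw that threatens the trial's conclusions.

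**What to change.** In SAP 9.6.2:

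1. Keep the existing combined row. Beside it add: (ALT or AST > 3 x ULN) and (TBL > 2 x ULN, or INR > 1.5 in subjects not on anticoagulation), with no ALP condition. Label it as the laboratory part of the protocol criterion.
2. List the subjects who meet the new row, with their baseline and alternative-cause status, so that the count can be reconciled with Table 11-2 and the serious adverse event reports.
3. State that CK and liver categories use the worst post-baseline value in the period (overall) or window (by visit), including unscheduled and local results judged against the local ULN. Exempt these categories from the closest-record rule.
4. Define when components of a combined row count as concurrent, and assess each combined row within such a set of values. Otherwise, in windows of up to 126 days, separate peaks could be joined, or a later high ALP could remove a case from the existing row.

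The cost is a few table rows, one listing and some programming. The analytes and concomitant therapies are already collected; whether local reference limits are captured should be checked. Rows at the temporary-withholding limits are optional. No clinical stopping, withholding or reporting rule is changed.

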9.6.3 Vital Signs

Vital signs will be summarized using descriptive statistics at each scheduled visit by actual treatment group.

9.6.4 Physical Measurements

Physical measurements will be summarized using descriptive statistics at each scheduled visit by actual treatment groups.

9.6.5 Electrocardiogram

The electrocardiogram (ECG) measurements from this clinical study were performed as per standard of care for routine safety monitoring, rather than for purposes of assessment of potential QT interval corrected (QTc) effect. Since these evaluations may not necessarily be performed under the rigorous conditions expected to lead to meaningful evaluation of QTc data; neither summaries nor statistical analyses will be provided, and these data would not be expected to be useful for meta-analysis with data from other trials.

9.6.6 Antibody Formation

Anti-olpasiran binding antibodies will be summarized descriptively, if applicable. Subject level listing may be provided instead of summary if there is a small number of subjects that are tested for anti-olpasiran antibodies.

9.6.7 Exposure to Investigational Product

The exposure to IP will be summarized using descriptive statistics by actual treatment group.

9.6.8 Exposure to Concomitant Medication

Number and proportion of subjects receiving medications of interest will be summarized by preferred term or category for each treatment group as coded by the World Health Organization Drug (WHODrug) dictionary.

9.7 Other Analyses

9.7.1 Analyses of Pharmacokinetic or Pharmacokinetic/Pharmacodynamic Endpoints

A PK sub-study will be conducted with a total of approximately 75 subjects (approximately 15 from each treatment cohort). A maximum of 3 samples may be collected at additional time points during the study if warranted and agreed upon between the investigator and

the sponsor. Pharmacokinetic samples will be collected as per the PK sub-study schedule of assessments (see protocol Table 1-1 and Table 1-2).

Individual and summary statistics for PK concentrations will be provided. These analyses will be performed by the CPMS group for the primary analysis, the end of treatment period analysis, and final analysis.

10. Changes From Protocol-specified Analyses

There are no changes to the protocol-specified analyses.

11. Literature Citations / References

Grundy SM, Stone NJ, Bailey AL, et al.

AHA/ACC/AACVPR/AAPA/ABC/ACPM/ADA/AGS/APhA/ASPC/NLA/PCNA guideline on the management of blood cholesterol: a report of the American College of Cardiology/American Heart Association Task Force on Clinical Practice Guidelines. *Circulation*. 2018; 139: e1046-e1081.

Dinko Rekic, Yaning Wang, Vikram Sinha. Request for Qualification of MCP-Mod as an efficient statistical methodology for model-based design and analysis of Phase II dose finding studies under model uncertainty. 22 April, 2015

12. Prioritization of Analyses

Not applicable.

13. Data Not Covered by This Plan

Not applicable.

14. Appendices

Appendix A. Analytical Study Week Assignments

Selected endpoints will be summarized by scheduled study visits in descriptive analyses. Since the actual visits may not exactly coincide with their scheduled visit day, the actual visit day is mapped to the study visit generally by non-overlapping consecutive intervals covering the entire time continuum. The mapping intervals for all distinct schedules are summarized in the following table.

Handling multiple records assigned to an analytical study week:

If there is more than one record in a study week interval, the analytical record for that specific study week will be defined as the record closest to the scheduled visit day of that specific study week ($7 \times \text{study week} + 1$). If two records are equidistant from the scheduled day, then the earlier record will be chosen. If there are multiple records on the same day, the last record will be used.

Analytical Study Week	Scheduled Visit Day	Physical, Neurological, and Muscular Examination, Vital Signs, Urine Pregnancy Test, Anti-Olpasiran-Antibody, PROMIS General Health	Physical measurement (weight only)	Fasting Lipids and Lp(a)	Glucose, ApoA1, ApoB, VLDL-C, Coagulation, Hematology, Hemoglobin A1C, Chemistry including hs-CRP, eGFR, Urinalysis
Day 2	2			(1, 15]	
Week 4	29			(15, 42]	(1, 56]
Week 8	57			(42, 70]	
Week 12	85	(1, 126]		(70, 98]	(56, 126]
Week 16	113			(98, 126]	
Week 20	141			(126, 154]	
Week 24	169	(126, 210]		(154, 182]	(126, 210]
Week 28	197			(182, 210]	
Week 32	225			(210, 238]	
Week 36	253	(210, 294]		(238, 266]	(210, 294]
Week 40	281			(266, 294]	
Week 44	309			(294, 322]	
Week 48	337	(294, 420]	(1, 420]	(322, 378]	(294, 420]
Week 60	421			(378, 462]	
Week 72	505	(420, 546]	(420, 546]	(462, 546]	(420, 546]
Week 84	589			(546, 630]	
Q12W ^a	n*7+1			((n-6)*7, (n+6)*7]	
> Week 72	Scheduled visit day	> 546	> 546	.. ^b	> 546

^a For Q12W scheduled visit, week n can have possible values of 96+12*m, where m=0, 1, 2, 3, ... until the subject **has completed study** or subject has discontinued from the study.

^b For Lipids and Lp(a), all visits occurred after week 84 will be mapped to Q12W window.

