1.3 Schedule of Activities (SoA)

Table 1-1. Schedule of Activities (Screening Through Week 24)

PROCEDURE	Screening (≤ 28 days before day 1)	Treatment Period: Screening to Week 24 (Duration of 48 weeks) ^a														
		Day 1			D2 + 2 days	W4 ± 3 days	W8	W12			W16 ± 3 days	W20	W24			W24 Phone call ^b
		Pre- dose	+1 hr	+3 hr				Pre- dose	+1 hr	Phone call ^b			Pre- dose	+ 1 hr	+3 hr	
GENERAL AND SAFETY ASSESSMENTS																
Informed consent	X															
Inclusion and exclusion criteria	X	X														
Demographics	X															
Physical, neurological, and muscular examination	X	X						X					X			
Physical measurements (body weight, height, waist circumference)		X														
Medical history	X	X														
ECG (single)		X						X					X			
Vital signs	X	X						X					X			
Survival status^c																
Adverse events		X	X	X	X	X	X	X	X	X	X	X	X	X	X	
Serious adverse events ^d	X	X	X	X	X	X	X	X	X	X	X	X	X	X	X	
Concomitant therapies review	X	X	X	X	X	X	X	X	X	X	X	X	X	X	X	
Randomization (after eligibility confirmed)		X														
LABORATORY ASSESSMENTS																
Serum pregnancy test (females of childbearing potential only) ^e	X															
FSH	X															
Urine Pregnancy Test (females of childbearing potential only) ^e		X						X					X			
Lipid Panel and Lp(a) ^f	X	X			X	X	X	X			X	X	X			
Fasting glucose	X	X				X		X					X			
Apolipoprotein A1 and Apolipoprotein B ^f	X	X				X		X					X			

Footnotes and abbreviations defined on last page of this table.

Table 1-1. Schedule of Activities (Screening Through Week 24)

PROCEDURE	Screening (≤ 28 days before day 1)	Treatment Period: Screening to Week 24 (Duration of 48 weeks) ^a														
		Day 1			D2 + 2 days	W4 ± 3 days	W8	W12			W16 ± 3 days	W20	W24			W24 Phone call ^b
		Pre- dose	+1 hr	+3 hr				Pre- dose	+1 hr	Phone call ^b			Pre- dose	+ 1 hr	+3 hr	
LABORATORY ASSESSMENTS CONTINUED																
Coagulation	X	X			X		X					X				
Hematology	X	X			X		X					X				
Hemoglobin A1C	X	X			X		X					X				
Chemistry including hs-CRP ^f	X	X			X		X					X				
eGFR	X	X			X		X					X				
Urinalysis	X	X			X		X					X				
Anti-olpasiran-antibody		X					X					X				
BIOMARKER ASSESSMENTS																
hs-IL-6 ^f		X														
Biomarker Discovery (eg, OxPL/ApoB and Lp(a) isoform)		X														
Biomarker Development (optional) ^g		X														
(OPTIONAL) PHARMACOGENETIC ASSESSMENTS																
Pharmacogenetic Development ^h		X														
PHARMACOKINETIC ASSESSMENTS																

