Olpasiran serum PK ⁱ		X	X	X		X		X	X			X	X	X		
CLINICAL OUTCOME ASSESSMENTS																
PROMIS General Health		X						X				X				
STUDY TREATMENT																
Olpasiran or placebo		X						X				X				

Footnotes and abbreviations defined on last page of this table.

Table 1-1. Schedule of Activities (Week 28 Through End of Study)

PROCEDURE	Treatment Period: Week 28 to Week 48 (Duration of 48 weeks) ^a									Extended Safety Follow-up ^k	End of Study
	W28	W32	W36			W36 Phone call ^b	W40	W44	W48	W60	W72 ^l
			Pre- dose	+1 hr	+3 hr	+ 1 day					
GENERAL AND SAFETY ASSESSMENTS											
ECG (single)			X					X			X
Physical, neurological, and muscular examination			X					X			X
Physical measurement (weight only)								X			X
Vital signs			X					X			X
Survival status^c									X		X
Adverse events	X	X	X	X	X	X	X	X	X	X	X
Serious adverse events ^d	X	X	X	X	X	X	X	X	X	X	X
Concomitant therapies review	X	X	X	X	X	X	X	X	X	X	X
LABORATORY ASSESSMENTS											
Urine Pregnancy Test (females of childbearing potential only) ^e			X					X			X
Lipid Panel and Lp(a) ^f	X	X	X				X	X	X	X	X
Fasting glucose			X					X			X
Apolipoprotein A1 and Apolipoprotein B ^f			X					X			X
Coagulation			X					X			X
Hematology			X					X			X
Hemoglobin A1C			X					X			X
Chemistry including hs-CRP ^f			X					X			X
eGFR			X					X			X
Urinalysis			X					X			X
Anti-olpasiran-antibody			X					X			X
BIOMARKER ASSESSMENTS											
hs-IL-6 ^f			X					X			X
Biomarker Discovery (eg, OxPL/ApoB and Lp(a) isoform)			X					X			X
Biomarker Development (optional) ^g			X					X			X

Footnotes and abbreviations defined on last page of this table.

Table 1-1. Schedule of Activities (Week 28 Through End of Study)

PROCEDURE	Treatment Period: Week 28 to Week 48 (Duration of 48 weeks) ^a									Extended Safety Follow-up ^k	End of Study	
	W28	W32	W36			W36		W40	W44			W48
			Pre-dose	+1 hr	+3 hr	Phone call ^b						
			± 3 days			+ 1 day		± 3 days			± 7 days	
PHARMACOKINETIC ASSESSMENTS												
Olpasiran serum PK ⁱ	X		X	X	X			X		X		(X) ^j
CLINICAL OUTCOME ASSESSMENTS												
PROMIS General Health			X							X		(X) ^j
Exit Survey										X		(X) ^j
STUDY TREATMENT												
Olpasiran or placebo			X									

Page 4 of 4

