8.1.2 Treatment Period

Visits will occur per the Schedule of Activities (Table 1-1). On-study visits may be completed within \pm 3 day, aside from Day 2 visit which may be completed + 2 day. The date of the first dose of investigational product is defined as day 1 and will occur on day of randomization. All subsequent doses and study visits will be scheduled based on the day 1 date, with the final day of the treatment period defined as week 48. Administration of investigational product is to be administered last during each visit that it is required, except when post-dose PK samples are being collected.

Telemedicine, paper PRO completion, and home healthcare visits may be implemented at randomization/day 1 onward, where circumstances outside the subject's, site's, and sponsor's control (eg, pandemic) result in study visits being unable to be conducted. The sponsor must authorize use of these approaches in advance of each visit, and this approach may only be used where allowable by local health authorities, ethics

committees, and healthcare provider guidelines (eg, hospital policies). The minimum possible number of visits should occur outside the clinic, and visits should return to “in-clinic” at the earliest possible opportunity.

Subjects that withdraw from study treatment should continue with on-study visits (see Section 7.1 for more details). If a subject withdraws from the study early, all efforts should be made to complete and report the observations as thoroughly as possible up to the date of withdrawal. The procedures for the EOS visit should be completed at the time of withdrawal (Section 8.1.4).

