9.5.3 Analyses of Exploratory Efficacy Endpoint(s)

Exploratory endpoints of percent change from baseline at scheduled visits in Lp(a), LDL-C and ApoB will be analyzed using repeated measures linear effects model including terms for treatment group, stratification factors, scheduled visit and the interaction of treatment group with scheduled visit will be used; and achievements of Lp(a) at scheduled visits (including achievement of Lp(a) < 125nmol/L) will be analyzed using CMH test as specified in Table 2. Subject incidence of positively adjudicated events (overall and by event type as defined in protocol) and change from baseline in PROMIS Global Health measures at scheduled visits will be summarized by treatment group using descriptive statistics.

Descriptive summary for non-HDL-C, HDL-C, VLDL-C and Triglycerides will be provided by scheduled visits.

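### SAP Appendix A windows VLDL-C with chemistry instead of with the lipid panel, so 9 of its 15 post-baseline visits drop out of the by-visit summary; a weight taken at early withdrawal is also shown as week 48

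*SAP*

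**What the plan says.** **VLDL-C.** SAP Appendix A assigns measurements to analysis weeks in four columns. VLDL-C stands in the fourth, "Glucose, ApoA1, ApoB, VLDL-C, Coagulation, Hematology, Hemoglobin A1C" and further chemistry items, with windows for weeks 4, 12, 24, 36, 48 and 72 and one bin beyond day 546. The Fasting Lipids and Lp(a) column has 15 windows from day 2 through week 72, then week 84 and 12-weekly windows.

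Elsewhere VLDL-C is a lipid. Protocol Table 11-1 lists it in the lipid panel. SAP 5.2 groups it with total cholesterol, HDL-C, LDL-C and triglycerides, and names ApoA1 and ApoB separately. Under the reflexive approach in SAP 5.3, ultracentrifugation LDL-C and VLDL-C come from the same blood sample. SAP 9.5.3 states: "Descriptive summary for non-HDL-C, HDL-C, VLDL-C and Triglycerides will be provided by scheduled visits".

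**Window rules.** Visits are "mapped to the study visit generally by non-overlapping consecutive intervals covering the entire time continuum". Where several records share a window, the analysis record "will be defined as the record closest to the scheduled visit day of that specific study week"; ties go to the earlier record.

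**Weight.** Protocol Table 1-1 schedules weight at day 1, week 48 and end of study. Appendix A gives it (1, 420] for week 48, (420, 546] for week 72, and a bin beyond day 546. Protocol 8.1.2 adds, for subjects who leave the study early: "The procedures for the EOS visit should be completed at the time of withdrawal". SAP 9.6.4 summarises physical measurements by scheduled visit and has no rule for weights taken at early exit.

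**The concern.** A programmer who follows Appendix A literally cannot produce the by-visit VLDL-C summary that SAP 9.5.3 describes. HDL-C, non-HDL-C and triglycerides would appear at 15 post-baseline visits through week 72, and VLDL-C from the same samples at six. If a target visit is missed, VLDL-C from a neighbouring visit fills the gap under the target's label, while LDL-C from that same sample keeps its own week.

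For weight, the week 48 summary can include a value measured much earlier in a subject who left the study, with nothing in the table to show it.

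What is at stake is whether descriptive tables are complete and correctly labelled. No hypothesis test is involved.

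**Working it through.** **1. Reproduce the plan's windows.** Take scheduled day = 7 × week + 1 (day 2 for the Day 2 visit), open the first window after day 1, and set each upper bound to the midpoint between this scheduled day and the next, rounded up, minus 1.

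- Chemistry column: weeks 4 and 12 give (29 + 85)/2 − 1 = 56; weeks 12 and 24 give (85 + 169)/2 − 1 = 126; then 210, 294 and 420. Week 72 against week 84 gives (505 + 589)/2 − 1 = 546.
- Lipid column: day 2 and week 4 give 15.5, rounded up to 16, minus 1 = 15; weeks 48 and 60 give (337 + 421)/2 − 1 = 378.
- Weight column: with weeks 48 and 72 only, the first window runs from after day 1 to (337 + 505)/2 − 1 = 420.

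The rule returns every stated bound through week 84 in all four columns. The VLDL-C windows are therefore those of the chemistry schedule. The weight window follows from the weight schedule.

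**2. Count VLDL-C visits.** Post-baseline lipid-panel visits in Table 1-1: day 2 and weeks 4, 8, 12, 16, 20, 24, 28, 32, 36, 40, 44, 48, 60, 72 = 15. Windows in the column that holds VLDL-C, through week 72: 6. Without a window of their own: 15 − 6 = 9.

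**3. Follow each sample at its nominal day.**

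| VLDL-C window | Days | Width (weeks) | Lipid visits inside | Dropped if target present | Used if target missing |
|---|---|---|---|---|---|
| Week 4 | (1, 56] | 7.9 | Day 2, 4 | Day 2 | Day 2 |
| Week 12 | (56, 126] | 10 | 8, 12, 16 | 8, 16 | 8 |
| Week 24 | (126, 210] | 12 | 20, 24, 28 | 20, 28 | 20 |
| Week 36 | (210, 294] | 12 | 32, 36, 40 | 32, 40 | 32 |
| Week 48 | (294, 420] | 18 | 44, 48 | 44 | 44 |
| Week 72 | (420, 546] | 18 | 60, 72 | 60 | 60 |

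Dropped values: 1 + 2 + 2 + 2 + 1 + 1 = 9, as in step 2. In the week 12, 24 and 36 windows the two neighbours lie 28 days either side of the target, so at nominal days the tie rule takes the earlier one.

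Visit tolerances move two cases. A week 8 visit on days 54 to 56 falls in the week 4 window, and a week 60 visit on days 414 to 420 falls in the week 48 window.

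**4. One sample, two labels.** Suppose week 36 is missed and week 32 is attended on day 225. LDL-C falls in (210, 238] and is week 32. VLDL-C from that sample falls in (210, 294] and, with no week 36 record, is reported as week 36.

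**5. Beyond day 546.** Other lipids go to week 84 and the 12-weekly windows; VLDL-C goes to a single bin. This concerns the subjects whose end-of-study visit falls after week 72 (Table 1-1, footnote l).

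**6. Weight.** The later weight marks in Table 1-1 are read as week 48 and end of study, which agrees with the weeks in Appendix A's weight column. A withdrawal visit on day 36 would be labelled week 4 for lipids and chemistry, week 12 for vital signs and week 48 for weight, and the weight label is 337 − 36 = 301 days off. The extreme is 337 − 2 = 335 days.

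At the 5% drop-out in the sample size section, the ceiling is 0.05 × 58 = 2.9 per arm, or 0.05 × 290 = 14.5 overall.

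**The case against.** **VLDL-C.** The placement could be deliberate. The six chemistry visits are also the fasting-glucose visits, and Table 11-1 footnote a requires fasting only when that sample is taken. The protocol synopsis names very low-density lipoprotein apart from lipids, and SAP 9.5.3 does not list its visits. The SAP gives no such reason, however. A fasting rationale would apply equally to triglycerides, which Appendix A does not move, and Table 1-1 has no separate VLDL-C row. The inconsistency stands unless the SAP explains it.

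A reader might infer that VLDL-C values are routinely given the wrong visit, or that the lipid tables would contradict each other. The documents do not support that. When the target visit is present, the closest-record rule selects it, and VLDL-C then comes from the same visit as the other lipids. At the other nine visits it is absent, not contradictory.

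**Weight.** A reader might infer that the (1, 420] bound is a mistake, or that every weight after day 1 counts as week 48. Neither holds. The bound follows from the tiling convention and a schedule with no weight between day 1 and week 48. Other columns also open just after day 1, and later weights have their own windows. A completer's week 48 weight is kept because it is closest to day 337. What remains is the label on an early-exit weight. The convention is qualified by the word generally, so an exception is open to the sponsor.

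**Conclusion.** The VLDL-C placement in Appendix A conflicts with protocol Table 11-1, the schedule of activities, SAP 5.2 and SAP 9.5.3. The main effect is loss of 9 of 15 post-baseline visits through week 72 from the VLDL-C summary: day 2 and weeks 8, 16, 20, 28, 32, 40, 44 and 60. Mislabelling is a lesser effect, conditional on a missing target visit.

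The weight point is secondary. About 3 per arm is a ceiling. It assumes that the 5% planning figure holds and that every drop-out leaves by day 420, has a weight recorded at exit and has no week 48 weight. Subjects who only stop treatment are meant to stay on study, and those who die or are lost to follow-up would usually give no exit weight, so the real number should be smaller.

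Neither VLDL-C nor weight is a named endpoint, and both are only summarised descriptively. It would also be wrong to extend the point to ApoB because it shares the column: ApoB is drawn on that column's schedule, so its windows are right. The Lp(a) windows and all tested endpoints are unaffected. This is a minor correction, worth making because it is nearly free.

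**What to change.** - **VLDL-C:** move it in Appendix A from the chemistry column to the existing Fasting Lipids and Lp(a) column. This raises its windows through week 72 from 6 to 15 and gives it the same windows as LDL-C at every visit. If the sponsor intends the reduced schedule, state the reason in Appendix A and the six visits in SAP 9.5.3.
- **Weight:** add a sentence that weights taken at early withdrawal are reported separately. Alternatively, start the week 48 weight window after day 294, as for vital signs. That leaves days 2 to 294 unassigned, which departs from the tiling convention and should be stated, and a withdrawal on days 295 to 420 would still be labelled week 48.

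The cost is one analyte moved between two column headers, plus one sentence or one bound. No new data are needed, and power and timing do not change.
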